## **6.6 Other Safety Analyses**

### **6.6.1 Physical Examinations**

Physical examinations will be performed at screening and study exit visit. Abnormal findings will be summarized by BOTOX treatment group. No statistical tests will be performed.

### **6.6.2 Pregnancy Test Results**

Pregnancy test results for female patients will be provided in a data listing.

### **6.6.3 Post-void Residual (PVR) Urine Volume**

Summary statistics for mean values at each visit, baseline and mean change from study baseline, and 95% CI for the mean change from baseline at each applicable visit will be tabulated by treatment group.

As per the protocol guidance, patients with elevated PVR or patients who initiated clean intermittent catheterization (CIC) may have further specific follow-up visits where PVR and the need for CIC are evaluated. Therefore, these patients may have multiple post-baseline PVR values recorded within 1 visit window, and in those cases, the highest PVR value will be presented in the summary table.

The proportion of patients with total PVR urine volume of  $\leq 100$ ,  $> 100$  to  $< 200$ ,  $\geq 200$  to  $< 350$  and  $\geq 350$  mL will be summarized by treatment group and visit for each BOTOX treatment cycle.

### **6.6.4 Use of Clean Intermittent Catheterization Post-treatment**

A listing of patients will be produced for patients using CIC containing all data from the eCRF information page.

### **6.6.5 Bladder and Kidney Ultrasound**

A listing of all bladder and kidney ultrasound results will be provided for patients with at least 1 positive finding.

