6.3.11 Bladder and Kidney Ultrasound

Ultrasound of the bladder and kidneys will be performed during the screening period (which for this evaluation can include prior to randomization on day 1), at the qualification for retreatment clinic visit, and at the exit visit.

In the case of unclear new findings suggestive of stones (kidney, ureter, or bladder), other diagnostic measures must be performed to confirm the presence of stones (eg, x-ray with or without contrast, urogram, computed tomography scan, magnetic resonance imaging, or cystoscopy).

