7.3.4 Safety Analyses

All safety analyses will be conducted on the BOTOX-treated population. Safety variables are adverse events, serious adverse events, physical examination, vital signs, laboratory tests (urinalysis, hematology, and clinical chemistry), renal function (eGFR), PVR urine volume, use of CIC, kidney and bladder ultrasound, immunogenicity testing, concomitant medications, concurrent procedures, and a urine pregnancy test for females who are postmenarche.

Medical Dictionary for Regulatory Activities (MedDRA) nomenclature will be used to code adverse events. For each adverse event reported, the number and percent of patients will be tabulated based on the preferred term. The tables will be generated by relationship to treatment as well as by primary system organ class and severity.

Data will be presented by BOTOX treatment cycle and grouped according to the actual dose received at that treatment cycle (grouped to the nearest dose group [25 U, 50 U, or 100 U BOTOX]), as well as by an overall BOTOX group (ie, regardless of dose).

As described in Section 6.3.15, immunogenicity samples will be analyzed using a 2-step process (toxin-binding and toxin-neutralizing antibodies). Results from both steps will be presented.

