## 2.3 Data Conventions

The following data conventions will be applied to all analyses:

- Only data with exceptions will be listed for conciseness. For example, the following would not be listed: normal findings for medical history and physical examination, pregnancy tests results for males or females when not applicable, etc.
- The level of significance used for all statistical tests will be 0.05, 2-sided, unless stated otherwise. P-values ≤0.050 will be considered as statistically significant.
- The type III sums of squares will be used for all analysis of covariance models (ANCOVA) and analysis of variance models (ANOVA).
- The variance for Kaplan-Meier estimates will be calculated using Greenwood's formula.
- Descriptive statistics for continuous variables will include the sample size (n), mean, standard deviation (SD), median, minimum (min), first quartile (Q1), third quartile (Q3), and maximum (max).
- Summary statistics for categorical variables will include the sample size (n), frequency count and percent.

- The Medical Dictionary for Regulatory Activities (MedDRA) dictionary will be used to code all adverse events (AEs) and medical history.
- World Health Organization Drug Dictionary Enhanced (WHO DDE) preferred name and MedDRA will be used to code all medications.
- Study duration from randomization/day 1 will be calculated as:  
$$\text{Study days} = \text{visit date} - \text{randomization/day 1 visit date} + 1.$$
- The Cycle duration for treatment X will be calculated as:  
$$\text{Study days} = \text{visit date} - \text{treatment X date} + 1.$$
- The algorithm presented in [Table 3](#), together with the rules below will be used to impute incomplete or missing dates for adverse events and medications as follows:
  - (a) AE start dates will be imputed as the minimum of the following:
    - initial imputed date, where target date = first study drug injection date.
    - complete end date
  - (b) Medication start dates will be imputed as the minimum of the following:
    - initial imputed date, where target date = first study drug injection date – 1.
    - complete end date
  - (c) AE and Medication end dates will be imputed as the minimum of the following:
    - initial imputed date, where target date = study exit date + 30.
    - Death date
- For each treatment cycle, AEs will be counted with onset date between the day when the study treatment is received and the day before the next treatment is received or exit day.

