## 6. Safety Analyses

All analyses will be performed on the BOTOX-treated population. Adverse events and all other safety analyses will be presented by BOTOX treatment cycle in this population and grouped according to the actual dose received at that treatment cycle (25, 50, or 100 U of BOTOX as well as an 'All BOTOX' group).

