### 6.4 Clinical Laboratory Evaluations

The clinical laboratory data (hematology, blood chemistry, and urinalysis) will be summarized by BOTOX treatment group for each BOTOX treatment cycle. Descriptive statistics will be generated for baseline values and change from study baseline by visit. Study baseline is defined as the last assessment prior to treatment 1.

Clinical laboratory test values will be considered potentially clinically significant (PCS) if they meet either the lower-limit or higher-limit PCS criteria. PCS criteria are specified on [Table 4](#). The number and percentage of patients who have PCS postbaseline clinical laboratory values will be tabulated for each cycle by treatment group. The percentages will be calculated relative to the number of patients with available non-PCS study baseline values and at least 1 postbaseline assessment during the treatment cycle of interest. The numerator will be the total number of patients with available non-PCS baseline values and at least 1 PCS postbaseline value during the treatment cycle of interest. A supportive listing of patients with PCS postbaseline values will be provided, including the patient number, baseline and all postbaseline (including non-PCS) values.

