**Table 4 Clinical Laboratory PCS Criteria**

Laboratory Group	Parameter	SI Unit	PCS Low Limit	PCS High Limit
Hematology	Basophils, absolute cell count	10  /L	—	> 2.0 × ULN
	Eosinophils absolute cell count	10  /L	—	> 2 × ULN
	Hematocrit	%	< 0.9 × LLN	> 1.1 × ULN
	Hemoglobin	g/L	< 0.9 × LLN	> 1.1 × ULN
	Lymphocytes absolute cell count	10  /L	< 0.7 × LLN	> 1.3 × ULN
	Monocytes, absolute cell count	10  /L	< 0.5 × LLN	> 2.0 × ULN
	Neutrophils absolute cell count	10  /L	< 0.7 × LLN	> 1.5 × ULN
	Platelet count (thrombocytes)	10  /L	< 0.5 × LLN	> 1.5 × ULN
	Red blood cell count	10  /L	< 0.9 × LLN	> 1.1 × ULN
	White blood cell count	10  /L	< 0.9 × LLN	> 1.5 × ULN
Chemistry	Alanine aminotransferase	U/L	—	> 3 × ULN
	Alkaline phosphatase	U/L	—	> 1.2 × ULN: 5-11 years old > 3 × ULN: ≥ 12 years old
	Aspartate aminotransferase	U/L	—	> 3 × ULN
	Bicarbonate	mmol/L	< 0.9 × LLN	> 1.1 × ULN
	Bilirubin, total	µmol/L	—	> 1.5 × ULN
	Blood urea nitrogen	mmol/L	—	> 1.5 × ULN
	Calcium	mmol/L	< 0.9 × LLN	> 1.1 × ULN
	Chloride	mmol/L	< 0.9 × LLN	> 1.1 × ULN
	Creatinine	µmol/L	—	> 1.5 × ULN
	Glucose, nonfasting	mmol/L	< 0.8 × LLN	> 1.5 × ULN
	Phosphorus	mmol/L	< 0.9 × LLN	> 1.1 × ULN
	Potassium	mmol/L	< 0.9 × LLN	> 1.1 × ULN
	Magnesium	mmol/L	< 0.9 × LLN	> 1.1 × ULN
	Protein, total	g/L	< 0.9 × LLN	> 1.1 × ULN
	Sodium	mmol/L	< 0.9 × LLN	> 1.1 × ULN
Uric acid (urate)	µmol/L	—	> 1.2 × ULN	
Urinalysis	Glucose	µmol/L	—	Positive
	pH	—	< 0.9 × LLN	> 1.1 × ULN
	Protein	g/L	—	Positive
	Specific gravity	—	—	> 1.1 × ULN

LLN = lower limit of normal (value provided by the laboratory); SI = *Le Système International d'Unités* (International System of Units); ULN = upper limit of normal (value provided by the laboratory).

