### 6.6.7 Renal Function Testing

Renal function will be monitored from an estimate of the glomerular filtration rate (eGFR) determined from the serum creatinine levels obtained on the day of each treatment (prior to treatment), week 12 after each treatment, and at study exit. The calculation of eGFR will be based on  $eGFR = 0.41 \times \text{height (cm)}/\text{serum creatinine (mg/dL)}$ . For the derivation of estimated GFR, the height closest to the serum creatinine assessment will be used.

Summary statistics for mean values at each visit, study baseline and mean change from study baseline will be tabulated by treatment group. For study baseline eGFR, the latest value prior to the first treatment will be presented in the summary table.

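### New ultrasound findings and eGFR decline have no planned patient-level rate by dose: ultrasound is only listed, eGFR has only continuous summaries, and the creatinine flag catches only large losses

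*SAP*

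**What the plan says.** Protocol 7.3.4 names renal function (eGFR) and kidney and bladder ultrasound among the safety variables, and adds: "Data will be presented by BOTOX treatment cycle and grouped according to the actual dose received at that treatment cycle". SAP 6 carries this over: "all other safety analyses will be presented by BOTOX treatment cycle in this population and grouped according to the actual dose received".

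The two variables are then handled as follows.

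- **Ultrasound (SAP 6.6.5).** "A listing of all bladder and kidney ultrasound results will be provided for patients with at least 1 positive finding". No count, percent, denominator or comparison with screening is planned.
- **eGFR (SAP 6.6.7).** "Summary statistics for mean values at each visit, study baseline and mean change from study baseline will be tabulated by treatment group". There is no category of decline, and SAP Table 4 ("Clinical Laboratory PCS Criteria") has no eGFR row.

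SAP 2.3 widens the eGFR output. Its conventions cover all analyses: "Descriptive statistics for continuous variables will include the sample size (n), mean, standard deviation (SD), median, minimum (min"), followed by the quartiles and the maximum.

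For laboratory tests, SAP 6.4 does plan a patient-level rate: "The number and percentage of patients who have PCS postbaseline clinical laboratory values will be tabulated for each cycle by treatment group". Its denominator is patients with a non-PCS baseline and at least one later value in the cycle. In Table 4, creatinine and blood urea nitrogen are each flagged above 1.5 x ULN.

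On timing, Protocol 6.3.11 says "Ultrasound of the bladder and kidneys will be performed during the screening period", then again at the qualification for retreatment visit and at exit. Creatinine is drawn before each treatment, at week 12 after each treatment and at exit (Protocol 6.3.14.1).

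**The concern.** The trial has no control treatment (Protocol 5.2), so the comparison of doses is the only concurrent between-group safety comparison. Protocol 1 reports that residual urine, retention, urinary tract infection and catheterization were dose-dependent in the adult phase 2 study. That raised residual urine may affect the kidney or bladder wall is a clinical inference, not a statement in the documents. Still, the protocol collects scans and eGFR throughout and calls both safety variables.

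A structural change or a fall in filtration would probably show in a few patients rather than as a shift of the whole group. The useful summary is then how many patients, out of how many examined, at each dose. A listing restricted to patients with a positive finding omits everyone scanned and found clear, so it supplies no denominator. A continuous summary does not say how many patients declined. At stake is whether the report can state a rate, with its uncertainty, for either variable.

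**Working it through.** **Inputs from the documents**

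- eGFR = 0.41 x height / serum creatinine (Protocol 6.3.14.1, SAP 6.6.7).
- Creatinine flag: above 1.5 x ULN (SAP Table 4).
- Planned size: 32 per group plus 10% attrition (SAP 1.3). Check: 32/0.9 = 35.6, rounded up to 36; 3 x 36 = 108, as stated. The plan gives no figure of its own for ultrasound or eGFR rates.

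**Assumed, because the documents give no values**

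- f, the baseline creatinine divided by ULN: 0.5 to 1.0.
- Baseline eGFR: 100 to 120.
- Smaller groups after recruitment stopped (SAP 15): 15 to 20 per group, for illustration.

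**1. What each by-dose rate covers**

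| Planned rate | What it leaves out |
|---|---|
| Creatinine and blood urea nitrogen flags (SAP 6.4) | Declines that stay below 1.5 x ULN |
| Residual-volume categories (SAP 6.6.3) | Kidney structure and filtration |
| Urinary tract infection and other adverse events (SAP 6.2) | Findings not reported as adverse events |

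The study-specific adverse event definitions in Protocol 9.1.2 cover retention, residual urine and urinary tract infection. None covers an ultrasound finding or an eGFR fall.

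**2. eGFR loss needed to trigger the creatinine flag**

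With height and ULN constant, eGFR is proportional to 1/creatinine. The ratio of eGFR at the flag limit to baseline is f/1.5, so the loss is 1 - f/1.5.

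| f | Loss needed |
|---|---|
| 0.5 | 67% |
| 0.6 | 60% |
| 0.7 | 53% |
| 0.8 | 47% |
| 0.9 | 40% |
| 1.0 | 33% |

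Conversely, halving eGFR doubles creatinine to 2f x ULN, which is flagged only if f > 1.5/2 = 0.75. A 25% fall multiplies creatinine by 1/0.75 = 1.33 and is flagged only if f > 1.5 x 0.75 = 1.125, that is, from a baseline already above normal.

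**3. What the continuous summary shows**

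If k of 32 patients lose half of an eGFR of E, the mean moves by 0.5 x E x k/32.

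- k = 1: 1.6 (E = 100) to 1.9 (E = 120).
- k = 3: 4.7 to 5.6.

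The minimum shows the single worst value, not whether one patient or three lie near it.

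**4. What a rate would add**

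The exact two-sided 95% upper limit for 0 of n is 1 - 0.025^(1/n).

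| n | Upper limit for 0/n |
|---|---|
| 36 | 9.7% |
| 32 | 10.9% |
| 20 | 16.8% |
| 15 | 21.8% |

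For 3 of 32 the interval is 2.0% to 25.0%. At 36 per group, Fisher's exact test gives p = 0.054 for 5 versus 0 and p = 0.025 for 6 versus 0. These tables would describe, not test.

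**5. Timing**

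A post-treatment scan happens at qualification for retreatment, possible from week 12, or at exit, which is about week 96 for a patient who completes without retreatment. Scan time therefore depends on retreatment, which may depend on dose. The week 12 creatinine is scheduled at the same time in every dose group.

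**The case against.** The strongest case against is that these events are largely counted already. Creatinine, blood urea nitrogen, residual volume, urinary tract infection and adverse events all have rates by dose. Protocol 9.1.1 defines an adverse event broadly enough to take in an untoward new scan finding, and Protocol 6.3.11 requires further tests when a scan raises an unclear new suspicion of stones. The ultrasound listing covers all results of each listed patient, so new findings can be told from old, and with groups this small it can be counted by hand.

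Much of this stands, and it rules out three readings that a reader might infer:

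- That kidney and bladder safety has no patient-level rate by dose. SAP 6.2, 6.4 and 6.6.3 show otherwise.
- That eGFR is reported only as an average. SAP 2.3 adds the minimum, quartiles and maximum.
- That the SAP breaks the protocol, or that doses cannot be compared at all. Protocol 7.3.4 asks for presentation by cycle and dose, not for a percent for every variable. Severe losses can reach the creatinine table, and reported findings reach the adverse-event tables.

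What does not stand is the claim that these outputs fill the gap. None gives a rate of new ultrasound findings or of moderate eGFR decline. Hand-counting the listing yields a numerator only.

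Two further objections should shape the remedy. A crude percent of scan findings mixes unequal follow-up, a problem that SAP 6.2 handles for adverse events with a day 84 table. After cycle 1 the dose is chosen by the investigator (Protocol 5.5), so later cycles are not a randomised comparison.

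**Conclusion.** The point holds for two named safety variables. New ultrasound findings and patient-level eGFR decline have no planned rate by dose, and the existing rates cover them only in part. The creatinine flag requires an eGFR loss of roughly 40% to 67% at an assumed baseline of 0.9 to 0.5 x ULN, so a moderate decline passes unflagged. A halving of eGFR in one of 32 patients moves the mean by only 1.6 to 1.9.

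These sizes rest on assumed baseline creatinine and eGFR, and on constant height and ULN; growth would lower the required loss somewhat. Blood urea nitrogen may flag some further patients, but the documents give no formula linking it to eGFR.

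The gap is in reporting, not in data collection. It should be closed, but the gain is limited: the added rates will be descriptive and imprecise, more so if recruitment stopped well short of 108.

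**What to change.** **SAP 6.6.5.** Add n/N (%) by cycle and actual dose of patients with an ultrasound finding absent at screening.

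- N is patients scanned after treatment in that cycle.
- Count the qualification-visit scan in the cycle just completed.
- Show time from treatment to scan by dose.
- State whether a persisting finding is counted again in later cycles.

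**SAP 6.6.7.** Add n/N (%) of patients whose eGFR fell from study baseline beyond reporting cut-offs that the sponsor fixes before database lock.

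- Examples are 25% and 50%. The documents supply no cut-off, and these are for reporting only.
- Report the week 12 visit of each cycle and exit.
- N is patients with a study baseline and a value at that visit.
- List the patients concerned.

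**Both.** Treat cycle 1, with randomised doses, as the main dose comparison and later cycles as descriptive. Give exact confidence intervals and no tests. Keep the current listing and summaries.

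**Cost.** Two extra tables, one listing and some SAP wording, with no new procedure or data. The downside is small counts, which need cautious reading.

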### **6.6.6 Positive Urine Culture Events**

A listing of patients' urine culture results will be presented by treatment group.

### 6.6.7 Renal Function Testing

Renal function will be monitored from an estimate of the glomerular filtration rate (eGFR) determined from the serum creatinine levels obtained on the day of each treatment (prior to treatment), week 12 after each treatment, and at study exit. The calculation of eGFR will be based on  $eGFR = 0.41 \times \text{height (cm)}/\text{serum creatinine (mg/dL)}$ . For the derivation of estimated GFR, the height closest to the serum creatinine assessment will be used.

Summary statistics for mean values at each visit, study baseline and mean change from study baseline will be tabulated by treatment group. For study baseline eGFR, the latest value prior to the first treatment will be presented in the summary table.

### 6.6.8 Type of Anesthesia Used During Administration of The Study Drug

One or more of the following was used for each participant during administration of the study drug:

- Intraurethral local anesthetic gel
- Instillation of local anesthetic solution into the bladder
- Sedative
- General anesthesia

Within each treatment cycle, the number and percentage of participants taking each type of anesthesia will be presented by treatment group.

In addition, because participants can receive one or more of the above anesthesia options, participants will be summarized based on whether they received general anesthesia or no general anesthesia.

## 6.7 Subgroup Analyses for Safety Variables

The incidences of TEAEs occurring in treatment cycle 1 will be summarized by treatment group for each of the following subgroups: gender (male, female), race (White, Non-White), geographic region (North America vs. Other Regions), and type of anesthesia received (general anesthesia vs. no general anesthesia). The number and percentage of patients reporting TEAE in each treatment group will be tabulated by descending percentage of the preferred terms for each of the subgroups. Since the study design allows patients to request/receive retreatment from week 12 onward, only TEAEs observed prior to or on day 84 after the first study injection will be presented.

## 7. Pharmacokinetic Data Analyses

No pharmacokinetic samples will be collected.

## 8. Immunogenicity Data Analyses

Two methods will be used to analyze immunogenicity samples: the enzyme linked immunosorbent assay (ELISA) method to detect the toxin-binding antibodies and the mouse protection assay (MPA) to detect the toxin-neutralizing antibodies to BOTOX. In the ELISA step, samples will be analyzed using a toxin-binding assay to determine the presence of any toxin-binding antibodies. Only samples from patients who are positive for the presence of toxin-binding assay will be subsequently analyzed using the MPA to determine the presence of toxin-neutralizing antibodies. For the toxin-binding assay, immunogenicity data will be reported as negative, positive or inconclusive. The percent of patients who have a serum sample that is positive for binding antibodies, as assessed by the screening and immunodepletion steps, will be reported by BOTOX treatment group at baseline, week 12 and study exit. The titer values for all samples will also be summarized.

The toxin-neutralizing data will be reported as protected, not protected, or inconclusive for the mouse protection assay (MPA). Samples considered protected are those that contain neutralizing antibodies towards BOTOX and thus protect the mouse from the lethal effects of BOTOX. Samples considered not protected do not protect the mouse from the lethal effects of BOTOX. The final result will depend on the number of mice found dead or alive. If 3 out of 4 mice or more are found dead then the sample will be considered negative (not protected) for neutralizing antibodies; if the number of dead mice is less than or equal to 1, then the sample will be considered positive (protected) for neutralizing antibodies; if 2 mice are found dead, or if the assay results or sample integrity are in question, then the sample will be considered as inconclusive. Antibody test results will be summarized and tabulated by BOTOX treatment group and by visit. The percent of patients considered protected, not protected, or inconclusive for toxin-neutralizing assay will be reported.

A listing of antibody assay results will be provided for patients who had a positive toxin-neutralizing antibody result.

